9.3. Clinical Laboratory Evaluation

A central clinical laboratory will be used for this study. Laboratory-based AEs will be reported based on the Grading Scale for Laboratory AEs – Modified from FDA Grading Scale as Appropriate for Local Lab (Protocol Appendix 2).

Summary statistics of test results and change from Baseline test results will be done for all serum chemistries and hematology.

For serum chemistries and hematology, and urinary assessments where FDA vaccine grading scale is applicable (Protocol Appendix 2), maximum shift from Baseline in severity will be provided.

Urinalysis (dipstick) results will be listed and not summarized.

A listing of clinical laboratory test results outside the reference ranges will be provided.

Clinically significant (CS) values or CS change from baseline values were to be recorded as AEs at the discretion of the clinical and safety monitor.

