1.3.1. Non-Clinical Safety

The safety of Bris10 M2SR monovalent vaccine was evaluated in a Good Laboratory Practice (GLP)-compliant, repeat-dose toxicity study in ferrets. In that study (Battelle Study Number 37234E), male and female ferrets were intranasally administered Bris10 M2SR once on Days 1 and 28 at dosages of 1.1×10^7 or 1.1×10^8 50% tissue culture infective dose (TCID₅₀) using the clinical spray device (Teleflex VaxINator). Overall, there were no observed toxicities from the two administrations of vaccine. The M2SR H3N2 vaccine was considered well tolerated, with only a transient reduction in physical activity being observed after the initial administration of 1.1×10^8 TCID₅₀. No redness or swelling of the nares and no gross or microscopic lesions of tissues surrounding the administration site were notable after intranasal administration of Bris10 M2SR with either dose level. No vaccine-related effects were observed in either dose group in the physical examinations or on body weights, body temperature, food consumption, eye exams, clinical chemistry, hematology, urinalysis, or coagulation parameters, organ weights or gross pathology. The only vaccine-related finding was mild to moderate inflammation of the distal bronchioles and adjacent alveoli and the perivascular tissue, observed 2 days after the first and second administration of Bris10 M2SR (on Days 3 and 30), particularly in the high dose group. The inflammation was not associated with any adverse clinical signs, clinical pathology, gross pathology or organ weight changes and was transient in nature, completely resolving by the end of the 21-day recovery period.

In multiple non-GLP studies of M2SR-based constructs (including H1N1, H3N2, and H5N1), there was (a) no evidence of weight loss or clinical symptoms in ferrets after intranasal administration; (b) no adverse histopathologic findings in any of the respiratory organs or brains of ferrets; and (c) no transmission of vaccine virus in any ferrets (3 donors and 6 contacts).

There is no evidence of M2SR vaccine virus replication when organs and nasal washes were analyzed for presence of virus. Moreover, the M2SR construct deletion prevents reversion, as confirmed by >10 serial passages in permissive cells and blind passage in non-permissive cells and in mice.

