8.3.3. Safety Analyses

Safety and tolerability of the Bris10 M2SR and Sing2016 M2SR influenza vaccines as assessed by subject diaries, solicited and unsolicited AEs, vaccine -associated AEs, SAEs, safety labs, vital signs, and physical examinations.

Exposure

Vaccine exposure will be summarized by actual dose, % of expected dose, and % of subjects receiving the expected dose.

Adverse Events

Treatment-emergent AEs (local and systemic) will be summarized as N (%) with AEs, with related-AEs, and by worst severity.

Incidence of TEAEs will be reported by MedDRA-coded SOC, PT and maximum severity.

Incidence of most frequent TEAEs and most frequent treatment-related TEAEs will be reported by SOC and PT

Listings of subjects who died, discontinued the study due to an AE, or experienced an SAE will be provided.

Dose-site reactions will be presented by reaction and severity.

Post-administration of symptoms (memory aid) will be summarized by time point, worst occurrence, and days with symptoms.

Clinical Laboratory Tests

Biochemistry and hematology laboratory results and change from baseline results will be summarized by timepoint using descriptive statistics.

Shift tables of maximum grade compared to baseline tabulated according to the FDA guidance: Toxicity Grading Scale for Healthy Adult and Adolescent Volunteers Enrolled in Preventive Vaccine Clinical Trials, or in accordance with the normal ranges of the clinical laboratory (below, within, or above normal range) for parameters for which no toxicity grades are defined.

A listing of clinical laboratory test results outside the reference ranges will be provided.

Vital Signs

Vital sign results and change from baseline results will be summarized by timepoint using descriptive statistics.

Limited Physical Examination

Abnormal findings in physical examination will be listed.

Pregnancy

A listing of pregnant subjects will be displayed.

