APPENDIX 2: LABORATORY ASSESSMENTS

- Urine drug screen^a
- Serology^a: HIV, HCV, HbsAg
- Urinalysis: Dipstick: specific gravity, pH, glucose, protein, blood, ketones, bilirubin, urobilinogen, nitrite, leukocyte esterase
In case of positive dipstick results, the sediment will be examined microscopically for red blood cells, white blood cells, and epithelial cells. Crystals, casts, and bacteria will only be reported if they are present.
- Hematology: Hemoglobin, white blood cells with differential (including neutrophils, lymphocytes, and eosinophils), platelets
- Biochemistry: Albumin, alkaline phosphatase, alanine aminotransferase, aspartate aminotransferase, bicarbonate (or carbon dioxide), calcium, chloride, potassium, sodium, lipid panel^a (total cholesterol, high-density lipoprotein cholesterol, low-density lipoprotein cholesterol, and triglycerides), total bilirubin, direct bilirubin^b, total protein, creatinine, C-reactive protein, creatine kinase, blood urea nitrogen (or urea)
- At screening, a urine pregnancy test will be performed for women of childbearing potential
- At the indicated time points, a urine pregnancy test will be performed for women of childbearing potential

a. At screening only.

b. To be assessed if total bilirubin is elevated above normal range.

Grading Scale for Laboratory AEs

Please score items based on the following guidance (from FDA Guidance for Industry: Toxicity Grading Scale for Healthy Adult and Adolescent Volunteers Enrolled in Preventive Vaccine Clinical Trials):

Serum*	Mild (Grade 1)	Moderate (Grade 2)	Severe (Grade 3)	Potentially Life Threatening (Grade 4)**
Sodium – Hyponatremia mEq/L	132 – 134	130 – 131	125 – 129	< 125
Sodium – Hypernatremia mEq/L	144 – 145	146 – 147	148 – 150	> 150
Potassium – Hyperkalemia mEq/L	5.1 – 5.2	5.3 – 5.4	5.5 – 5.6	> 5.6
Potassium – Hypokalemia mEq/L	3.5 – 3.6	3.3 – 3.4	3.1 – 3.2	< 3.1
Glucose – Hypoglycemia mg/dL	65 – 69	55 – 64	45 – 54	< 45
Glucose – Hyperglycemia Fasting – mg/dL Random – mg/dL	100 – 110 110 – 125	111 – 125 126 – 200	>125 >200	Insulin requirements or hyperosmolar coma
Blood Urea Nitrogen BUN mg/dL	23 – 26	27 – 31	> 31	Requires dialysis
Creatinine – mg/dL	1.5 – 1.7	1.8 – 2.0	2.1 – 2.5	> 2.5 or requires dialysis
Calcium – hypocalcemia mg/dL	8.0 – 8.4	7.5 – 7.9	7.0 – 7.4	< 7.0
Calcium – hypercalcemia mg/dL	10.5 – 11.0	11.1 – 11.5	11.6 – 12.0	> 12.0
Magnesium – hypomagnesemia mg/dL	1.3 – 1.5	1.1 – 1.2	0.9 – 1.0	< 0.9

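### SAP 9.3 omits the protocol's normal-range shift tables, so C-reactive protein, chloride and bicarbonate get no by-arm count of subjects moving from normal to abnormal, and SAP Section 12 does not declare the change

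*SAP*

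**What the plan says.** Protocol 8.3.3 (Safety Analyses, Clinical Laboratory Tests) plans shift tables of maximum grade against baseline. These use the FDA vaccine toxicity scale or are tabulated "in accordance with the normal ranges of the clinical laboratory (below, within, or above normal range) for parameters for which no toxicity grades are defined". The synopsis carries the same rule.

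SAP 9.3 plans three things for chemistry and hematology:

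- Summaries: "Summary statistics of test results and change from Baseline test results will be done for all serum chemistries and hematology".
- Shifts, for chemistry, hematology and "urinary assessments where FDA vaccine grading scale is applicable (Protocol Appendix 2), maximum shift from Baseline in severity will be provided".
- A listing of results outside the reference ranges.

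SAP 9.3 mentions no normal-range shift. SAP 1.1.1 says the plan is based on protocol v8.0, the version that contains both halves of the rule. SAP Section 12 lists the early halt to enrollment, the telephone Day 209 visits, and the cellular immunity and shedding data that were not available at lock. It does not mention shift tables.

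The Appendix 2 biochemistry panel includes "total protein, creatinine, C-reactive protein, creatine kinase, blood urea nitrogen (or urea" as well as chloride and bicarbonate (or carbon dioxide). None of C-reactive protein, chloride and bicarbonate carries the screening-only footnote.

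**The concern.** Safety is the primary objective, and the protocol gave every laboratory analyte one of two routes to a shift table. The SAP closes one of them without saying so. For an analyte with no grade, the remaining displays do not say how many subjects in each arm were normal at baseline and abnormal after dosing.

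Summary statistics cannot supply that count. With about 40 subjects per arm (SAP Section 12), the median describes the middle of the group, the maximum describes one subject, and the mean mixes the number of subjects who moved with how far they moved. The listing holds the individual values but leaves the reader to count by arm. It also shows only out-of-range results, so a subject listed only after dosing may have had a normal baseline or a missing one.

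**Working it through.** The plan gives no figure to reproduce, and no power or alpha calculation applies. The check compares the two shift rules and then sets the Appendix 2 panel against the Appendix 2 grading tables.

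**Step 1: the two rules**

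| Type of analyte | Protocol 8.3.3 and synopsis | SAP 9.3 |
|---|---|---|
| Has an FDA grade | Shift in maximum grade | Maximum shift in severity |
| Has no FDA grade | Shift below / within / above normal range | Not mentioned |

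**Step 2: can the SAP sentence be read more widely?** The clause about where the FDA scale applies may qualify only the urinary assessments and leave chemistry and hematology unrestricted. The table would still show a shift in severity, and an analyte with no grade has no severity. Both readings give the same result.

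**Step 3: which analytes are affected?** Leaving out the lipid panel (screening only), Appendix 2 lists 16 biochemistry analytes. Checked against the tables under "Grading Scale for Laboratory AEs":

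- With a grade row, 12: albumin, alkaline phosphatase, ALT, AST, calcium, potassium, sodium, total bilirubin, total protein, creatinine, creatine kinase, blood urea nitrogen.
- With no grade row, 3: C-reactive protein, chloride, bicarbonate.
- Conditional, 1: direct bilirubin, measured only when total bilirubin is raised, with no row of its own.

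12 + 3 + 1 = 16, so 3 of 16 routinely measured chemistries lose the display. The six named hematology parameters all have a grade row. I do not extend the point to ungraded dipstick items, because SAP 9.3 states expressly that dipstick results are listed and not summarized.

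**Step 4: are the data there?** Protocol Table 3 schedules chemistry at screening, Day 1 (baseline) and Days 8, 29 and 36, which gives three post-dose draws. Day 29 is after the first dose and before the second.

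**Step 5: what each ungraded analyte receives**

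| Display | Protocol | SAP |
|---|---|---|
| Summary of result and change from baseline | Yes | Yes |
| Listing of out-of-range results | Yes | Yes |
| AE record if judged clinically significant | Yes (6.2.2) | Yes (9.2, 9.3) |
| Count of normal-to-abnormal shifts by arm | Yes (8.3.3) | No |

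**The case against.** The strongest reply is that little is lost. Chemistry results and changes are summarized for every analyte. Protocol 8.1 presents tables by treatment and includes the median, minimum, maximum, standard error and a 95% interval. A value judged clinically significant becomes an adverse event and, if treatment-emergent, enters the by-arm tables by system organ class and preferred term. The primary endpoints are vaccine-associated adverse events, not laboratory shifts, and the trial is descriptive. The SAP is also silent on the normal-range rule rather than cancelling it, and the table shells that the protocol promises are not in the documents reviewed.

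Much of this stands, and it sets the size of the point. It does not remove it. Adverse event capture depends on judgement case by case, so it is not a systematic count. Unseen shells might include the missing table, but the SAP text does not call for one.

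A reader might infer that a dose-related rise in C-reactive protein would be hidden from every by-arm table. The summaries and the adverse event tables show otherwise. A reader might also treat C-reactive protein as the only inflammation marker measured. The documents do not describe it so, and the panel also has white cells with differential and albumin, which are graded and keep their shift tables.

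It is also tempting to tie the gap to the ferret study, where "The only vaccine-related finding was mild to moderate inflammation of the distal bronchioles and adjacent alveoli and the perivascular tissue". Protocol 1.3.1 reports that this inflammation was transient and came without clinical pathology change, so it gives no ground to expect a C-reactive protein signal. That study used Bris10 M2SR at up to 1.1×10^8 TCID50. Here Bris10 is given at 10^8, and only Sing2016 reaches 10^9, so a dose comparison would cross products as well as species.

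**Conclusion.** The discrepancy is real and undeclared. Followed as written, SAP 9.3 gives no by-arm count of subjects shifting from normal to abnormal for C-reactive protein, chloride and bicarbonate, although the protocol plans one. The loss is one display for three analytes that keep their summaries, listing and adverse event capture.

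This is a minor correction to safety reporting. It is worth making because it concerns the primary objective and the protocol already specifies the table. No power, alpha, dose or clinical rule changes. The conclusion rests on the SAP text as supplied and assumes the table shells add nothing to it. The documents give neither a C-reactive protein distribution nor an upper limit of normal, so I put no number on how large a rise the summaries could miss.

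**What to change.** Add one sentence to SAP 9.3, restoring the protocol's rule:

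> For analytes with no FDA grade (C-reactive protein, chloride, bicarbonate), shift from baseline to worst post-dose value by below/within/above normal range will be tabulated by treatment, using all scheduled post-dose draws (Days 8, 29 and 36).

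Chloride and bicarbonate can leave the range in either direction, so the shell should state how a subject with both a low and a high value is counted. If the sponsor prefers to leave the table out, SAP Section 12 should declare the omission and give the reason.

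The cost is one sentence and one more run of a standard shift table on data already collected. Nothing further is needed for the C-reactive protein summaries: the median is already planned, and quartiles or a geometric mean ratio would be a matter of preference.

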9.4. Vital Signs

Blood pressures, heart rate, respiratory rate and temperature will be summarized at each time point by descriptive statistics for the result and for the change from baseline

CS values or CS change from Baseline were recorded as AEs at the discretion of the clinical investigator.

9.5. Limited and Targeted Physical Examinations

A physical exam to determine the subject's suitability for the study was done prior to IP administration. Limited physical examinations consisting of nasal, lung and throat assessments were done predose, and at 5 and 30 minutes post dose on Days 1 and 29, and at Days 8, 36, 57 and 209. At the discretion of the Investigator, targeted physical examination may have been performed on other body systems and findings may be recorded as AEs. Physical examination findings will be included in the listings.

9.6. Halting Rules (Protocol Section 7.3)

Events meeting the halting rule criteria will be listed by subject and treatment.

10. HYPOTHESES TO BE TESTED

No formal hypotheses are to be tested. P-values are descriptive only.

11. DETERMINATION OF SAMPLE SIZE

The sample size of 50 subjects per group was chosen based on reports of studies of other vaccines in early stage development. This study is not powered for any formal treatment comparisons.

12. CHANGES IN THE CONDUCT OF THE STUDY OR PLANNED ANALYSES

The study was planned to enroll 50 subjects per treatment group. Enrollment was halted at approximately 40 subjects per group due to seasonal flu considerations.

Due to COVID-19 some Day 209 follow-up visits were conducted by telephone.

Secondary and exploratory endpoint data for CMI (ELISPOT) and viral shedding (influenza A-specific q-PCR) data were not available for analysis at database lock.

These and additional exploratory study endpoints may be the subject of future analyses.
